# 7.5. Randomization and Blinding

Not applicable.

# 7.6. Study Drug Supply, labelling, dispensing and handling

#### 7.6.1. Study Drug Supply

The Sponsor will supply encorafenib and binimetinib throughout the study period and once ended the trial to those patients who are benefiting of study treatment, as long as, medication be available for this trial by the manufacturer of the IMPs. In case that the study is suspended or completed while there are still patients under treatment with COMBO 450, the investigator or responsible should evaluate both patient's clinical status to confirm that disease is controlled and then inform to the sponsor who will make sure that based on the available information of the efficacy of the treatment, current availability of the investigational medical product and the potential benefit for the patient, will ensure that the patient continues with treatment as long as there is clinical benefit from it.

The Investigator or responsible site personnel must instruct the patient or caregiver to take the study drug as per protocol. Study drug(s) will be dispensed to the patient by authorized site

personnel only. All dosages prescribed to the patient and all dose changes during the study must be recorded on the patient record and the eCRF.

# 7.6.2. Study drug labelling

All drugs (encorafenib and binimetinib) will be open label. Medication labels will be in the local language and comply with the legal requirements of each country, including storage conditions for the drugs, batch number and expiration date, among others. The patient number should be hand-written by the investigator or its staff at the drug delivery time.

# 7.6.3. Study drug storage

Study treatments must be received by designated personnel at the study site, handled and stored safely and properly, and kept in a secured location to which only the Investigator and designated site personnel have access.

Upon receipt, the study drugs should be stored according to the instructions specified on the drug labels and Investigator's Brochure for encorafenib and binimetinib. Study medication is to be stored in a secure locked area while under the responsibility of the Investigator. Receipt and dispensing of study medication must be recorded by an authorized person at the Investigator's site.

Records of drug formulation, batch number, and number of blisters dispensed must be recorded in the IWRS system elaborated for this trial and in pharmacy source records.

#### 7.7. End of treatment

End of treatment is defined as the last visit where the decision is made to discontinue treatment. All required procedures of the Final Visit schedule may be completed within ±7 days of the end of treatment visit. Repeat disease assessment is not required if performed within 28 days prior to the end of treatment visit.

# 8. STUDY ASSESSMENTS

# 8.1. Schedule for tests and determinations

Table 11. Schedule for tests and determinations

Visit	Baseline (D-28 to D-1)	w4	w8 (D-56)	Every 4w	Every 8w	Every 12 w	End of treatment (28 +/-4d)	FU before DP	FU after DP for OS
Informed consent	Х								
Screening registration	Х								
Histology confirmation of disease	Х								
BRAF Status	×								
Anamnesis	Х								
Demographics	Х								
Physical examination / vital signs	х	Х	х	Х			Х		
ECOG PS	×	Х	х	Х			X	Х	
Basic neurologic examination and Modified Barthel Index	Х	Х	X	Х			X	×	
Ophthalmologic anamnesis an evaluation by Oncologist	Х	X	X	Х			X		
Ophthalmologist exploration	If clinical suspicion								
ECG	×	Х				Х	×		
LVEF (as per institutional guidelines)	X					Х			
Concomitant medications	×	Х	Х	Х			Х		
Inclusion/exclusion criteria	×								
QoL	×	X at weeks 8 and 24							
Analytical tests									
Clinical laboratory test	×	Х	Х	Х			X	Х	
Pregnancy test	Х			Х			×		
Disease evaluation									
Abdominopelvic CT Scan (1)	Х		Х		X (³)			X (every 8w) (³)	
Brain MRI (  )	х		Х		X (³)			X (every 8w) (³)	

Colour Digital Photography (including a metric ruler) of skin lesions (¹)	х		Х		X (³)			X (every 8w) (³)	
Safety evaluation									
Adverse events and Serious Adverse events		Every 4 weeks throughout all the study (From ICF signature up to EoT visit)							
Study Treatment									
COMBO450 follow-up and dispensing		Х		х					
Dose reduction		Throughout all the study, when applicable							
Dose delay		Throughout all the study, when applicable							
Long term FU									
OS Follow-up									Х
New anti-cancer therapy									Х

 $(^1)$  Out of the assessments indicated by protocol, patients can be assessed whenever the investigator considers it indicated.

 Contrast enhanced MRI.

 $(^3)$  Assessments will be done every two months up to 12 months, thereafter, patients will be assessed as per institutional criteria.

# **Protocol specifications for trial determinations**

**Informed Consent Form (ICF):** Determinations performed by routine clinical practice before signing the informed consent will be valid, provided they are carried out following from this protocol, if they have been performed during the period included in the table 11.

**Screening registration:** Any patient that sign ICF should be registered in the EDC system and have assigned a unique screening number.

**Anamnesis:** to be performed during the baseline period in the 2 weeks prior to inclusion. Medical history will include all active conditions and any condition diagnosed considered to be clinically significant by the investigator. Melanoma history will be recorded separately and not listed as Medical History.

**Demographics:** Date of birth, race, and sex.

**Physical examination/vital signs:** Complete physical examination, weight, height, and vital signs (pulse, respiratory rate, **blood pressure** and body temperature).

**ECOG-PS:** Functional status will be assessed using the ECOG score.

**Neurological examination:** Basic neurological assessment according to normal practice and Modified Barthel Index according to "Guidelines for the Modified Barthel Index of Activities of Daily Living"

**Ophthalmologic anamnesis and evaluation by Oncologist:** ophthalmologic anamnesis and evaluation performed by oncologist as a part of physical examination and it will be performed at baseline and in every monthly visit. Only if there's any alarm symptom or sign or previous ocular antecedents, patient will be evaluated by Ophthalmologist.

**Ophthalmologist examination:** Patient will be evaluated by Ophthalmologist if there's any alarm symptom or sign or previous ocular antecedents.

**ECG:** Standard 12-lead ECG at baseline, after 4 weeks of treatment, after every 12 weeks and in the end of treatment visit. Additional ECGs may be performed at the discretion of the investigator.

**Concomitant medication:** All drugs taken within 30 days before starting the trial and concomitantly during the study will be recorded in medical records and in eCRF with indication, dose information and administration dates.

**Inclusion and Exclusion Criteria:** Verification that patients meet all inclusion criteria and none of exclusion.

Quality of Life: EORTC QLQ 30 administered at baseline, at week 8 and week 24.

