## 7.1.4. Radiation therapy 

## 7.1.4.1 Whole Brain Radiation Therapy

- 1. Total Dose:
  - The whole brain planning target volume (PTV) will receive 30 Gy in 10 fractions.
  - Treatment will be delivered once daily, 5 fractions per week, over 2 to 2.5 weeks.
  - 2. Immobilization, Simulation, Localization:
    - Patients will be treated in the supine position using an adequate immobilization (aquaplast mask).
    - A treatment-planning CT scan of the whole head region must be acquired with the
      patient in the same position and immobilization device as for treatment. Axial slice
      thickness not exceeding 3-5 mm will be required. Contrast IV and MRI-CT fusion are
      not necessary.
  - 3. Target volumes:
    - It is not necessary to define the Gross Tumour Volume (GTV).
    - The Clinical Target Volume (CTV) is defined as the whole brain parenchyma to C1 (if no posterior fossa metastasis) or C2 (if MRI evidence of posterior fossa metastasis).
    - The PTV is defined as the CTV + 0.5 cm with clip at patient surface.
  - 4. Treatment Planning:
    - Treatments must be delivered with 3-D planning through parallel opposed fields that cover the entire cranial contents (also it is allowed static or dynamic intensity modulation).
    - All portals will be treated daily.
    - Treatment will be delivered using megavoltage machines with photon beams ranging from 4 to 8 MV. Electron, particle, or implant therapy is not permissible.

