**Toxicity of the combination after local treatment:** Number of patients with adverse events and serious adverse events, changes in laboratory values, vital signs, electrocardiograms (ECGs), LVEF (MUGA (Multigated Acquisition Scan) / echocardiogram) and assessment of physician, dermatological and ocular examinations graded according to the National Cancer Institute (NCI) Common Terminology Criteria for Adverse Events (CTCAE) v 4.03 after local treatment (after end of local treatment date). It will be studied using descriptive statistics techniques, such as frequency tables and contingency tables. The final statistical analysis of this endpoint is expected to be performed within 6 months after database closure expected at 24 months after last patient inclusion, however interim analysis might be performed when analysing other primary variables.

**Quality of life:** Change from baseline in the global health status score of the EORTC QLQ-C30. The final statistical analysis of this endpoint is expected to be performed within 6 months after database closure expected at 24 months after last patient inclusion, however interim analysis might be performed when analysing other primary variables.

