### 2.1.1.GLOBAL HEALTH STATUS/QoL 2.1.1.1. QL - GLOBAL HEALTH STATUS/QoL (REVISED) (FROM 2 ITEMS)

Table 1: Global health status/QoL

Global health status/QoL	N	Mean(SD)	Median(Min-Max)	p-value (wilcoxon test) compared with baseline
Baseline				
w8				
w16				

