#### 3. COHORTS A-C (SYMPTOMATIC PATIENTS)

Analyses were conducted exclusively on significant variables across the entire sample.

3.1.1.GLOBAL HEALTH STATUS/QoL

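### The protocol schedules quality of life at week 24, but all 40 SAP quality-of-life tables show week 16 instead; a significance filter also removes 12 of 16 scores from groups A+C and B.

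*Combined protocol and SAP*

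**What the plan says.** **Schedule.** The protocol states the same plan each time: the Synopsis (Quality of Life), the determinations text in section 8.1 ("EORTC QLQ 30 administered at baseline, at week 8 and week 24") and the QoL row of Table 11 ("X at weeks 8 and 24"). The visit lists in section 8.2 agree. QoL appears at baseline and at week 8, and among the 8-weekly visits it is restricted to week 24.

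**Endpoint.** Section 4.2 lists quality of life as a secondary objective in both cohorts. Section 10.2 defines the measure as "Change from baseline in the global health status score of the EORTC QLQ-C30" and names no time point.

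**SAP tables.** SAP sections 4.8 and 4.9 (cohort 2, Tables 108–123) and the separate QoL report (Tables 1–24) use one template throughout: rows for baseline, w8 and w16, with a column headed "p-value (wilcoxon test) compared with baseline". No text explains the w16 row.

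**Filter.** Section 3 of the QoL report (groups A+C) and section 4 (group B) carry the same sentence: "Analyses were conducted exclusively on significant variables across the entire sample". No significance threshold, time point or multiplicity adjustment is given for that selection.

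**The concern.** Section 5.3 makes the scan after 56 days the decision point for radiotherapy, so the week-8 questionnaire falls at that decision. Week 24 is then the only scheduled questionnaire that can describe patients after local treatment. A table set with no week-24 row either leaves that result out or reports it under the wrong week. A reader could not tell how long after radiotherapy the patients were asked.

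The filter raises a different problem. Groups A+C and B together make up the whole sample, so choosing scales by their whole-sample p-value and then showing those scales in the subgroups uses the same data twice. Changes on the retained scales tend to be exaggerated. A scale that improved in one group and worsened in the other can be flat overall and so be dropped, although such a contrast is what a subgroup table should reveal. The sentence is in the past tense, which suggests the choice was made after results were known.

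**Working it through.** The plan states no sample size, power or alpha for quality of life, so there is no QoL figure to reproduce. The check is a count, a timing calculation and an estimate of the filter's bias.

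**1. Tables and rows**

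| Set | Tables | Number | With w16 | With week 24 |
|---|---|---|---|---|
| Cohort 2 (SAP 4.8–4.9) | 108–123 | 16 | 16 | 0 |
| All patients (QoL report 2) | 1–16 | 16 | 16 | 0 |
| Groups A+C (QoL report 3) | 17–20 | 4 | 4 | 0 |
| Group B (QoL report 4) | 21–24 | 4 | 4 | 0 |
| Total | | 40 | 40 | 0 |

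This is one label repeated 40 times, not 40 separate errors. It affects one of two post-baseline time points.

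**2. Timing.** The difference between the two labels is 24 − 16 = 8 weeks. For whole brain radiotherapy the protocol says "Treatment will be delivered once daily, 5 fractions per week, over 2 to 2.5 weeks". Take a patient who starts at week 8 and needs 2.5 weeks:

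- radiotherapy ends at 8 + 2.5 = week 10.5;
- week 16 is 16 − 10.5 = 5.5 weeks after the end;
- week 24 is 24 − 10.5 = 13.5 weeks after the end.

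**3. Scores removed.** The full set is 1 global + 5 functional + 3 symptom + 6 single-item + 1 summary = 16. Sections 3 and 4 of the QoL report show four: global health status, emotional functioning, insomnia and the summary score. So 16 − 4 = 12 (75%) are absent in each section, and 12 × 2 = 24 subgroup tables are missing.

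**4. Size of the screen.** The whole-sample tables contain 16 scores × 2 time points = 32 comparisons with baseline. At an assumed 0.05 each, 32 × 0.05 = 1.6 false positives are expected if nothing changes. If the tests were independent, the chance of at least one would be 1 − 0.95^32 = 0.81. The scores are correlated, so 0.81 is only an illustration.

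**5. Bias on a retained scale with no true change.** Assume selection at two-sided p<0.05, one test per score and n paired questionnaires. Under normal theory the mean of |Z|, given |Z| > 1.96, is φ(1.96)/0.025 = 2.338. The expected spurious change in the selected direction is therefore 2.338/√n SD. If the true change is the same in both subgroups, the expected spurious change in each subgroup equals that in the whole sample.

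| n | 2.338/√n | Simulated paired Wilcoxon test, subgroup mean |
|---|---|---|
| 30 | 0.43 SD | 0.40–0.42 SD |
| 40 | 0.37 SD | 0.35 SD |
| 63 | 0.29 SD | 0.28–0.29 SD |

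The simulation used normal changes with true mean 0, a 60/40 subgroup split and 20,000 runs per n. The upper n is the planned total, 48 + 15 = 63; the lower n is an assumption.

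**6. Bias when there is a true change.** The same theory gives inflation of about 0.18 SD (n=30) and 0.07 SD (n=63) for a true change of 0.3 SD. For a true change of 0.5 SD it gives about 0.07 and 0.01 SD. The 0.3 to 0.4 SD figure therefore describes the null case only.

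**The case against.** The mismatch in weeks cannot be explained away. The nearest thing to flexibility is in section 8.2 f), which lets questionnaires follow normal practice for patients who stopped treatment before progression. That would not produce a uniform w16 row in every table. It is also fair that 5.5 and 13.5 weeks apply only to a patient irradiated straight after the week-8 scan. The protocol fixes no start interval, complete responders need not be irradiated, and radiosurgery has its own schedule. The 8-week difference does not depend on any of this.

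The case against the filter point is stronger:

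- Group A is cohort 2, and Tables 108–123 show all 16 scores for it without filtering. All 16 are also shown for the whole sample. What is lost is the pooled A+C group and group B.
- Groups A, B and C come from the SAP section on analyses requested by the coordinator. They are not the protocol's cohorts, so the filtered output is exploratory.
- The filter is openly stated, and global health status survives it in both groups.
- The bias shrinks quickly once a true change exists, and nothing in the documents shows that any retained scale is null.

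All of this stands and makes the filter the secondary part of the point. It does not make the selection sound.

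The same comparison exposes a related gap: cohort 1 as enrolled has no QoL tables of its own, although the objective covers both cohorts.

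**Conclusion.** Both parts hold. The time-point mismatch is certain from the text and is the more serious: 0 of 40 tables carry the scheduled week-24 assessment, so as written the SAP omits the only planned quality-of-life result after week 8 or misdates it by 8 weeks. The documents cannot show which. The week-8 result is sound.

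The filter removes 12 of 16 scores in each of groups A+C and B and biases what is kept. The 0.3 to 0.4 SD figure assumes p<0.05, one test per score, 30 to 63 pairs and no true change; with a real change the bias is smaller.

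This should be corrected. It does not touch the primary conclusion, which rests on intracranial response, and quality of life carries no formal hypothesis or power.

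**What to change.** 1. Check the questionnaire dates in the eCRF before editing anything. Do not simply rename w16.
2. Give every QoL table rows for baseline, week 8 and week 24, assigned by actual questionnaire date. If genuine week-16 forms exist, keep them in a row marked off-schedule and add week 24.
3. Delete the significance filter from sections 3 and 4 of the QoL report.
4. Report the change from baseline in global health status with a 95% CI at weeks 8 and 24 for all patients and for each group, whatever the p-value. Include cohort 1 as enrolled, so that the objective is covered in both cohorts.
5. Show the other 15 scores descriptively.

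The cost is a date check and table edits, with no new data collection. Restoring the dropped scores adds 24 subgroup tables (12 × 2), and cohort 1 needs its own output. If week-24 forms were not completed, that row will show few or no patients, and the report should then say so.

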# **Clinical laboratory test:**

- **Complete haematology:** Complete blood count that includes total white blood cell count with leukocyte formula, haemoglobin, and platelet count.
- Complete serum biochemistry and urinalysis: including LDH, CK (CPK), gamma-glutamyltransferase (GGT), creatinine, creatinine clearance, , total bilirubin, alkaline phosphatase, aspartate aminotransferase (AST) or GOT, alanine aminotransferase (ALT) or GPT, Calcium (Ca), Potassium (K), and Magnesium (Mg).

The analytical studies may be performed up to 72 hours before the scheduled visits to have the results at the time of the patient's visit. Liver function tests, including GGT, ALT, AST and total bilirubin should be performed following the indications of "schedule of determinations" and when clinically indicated, with more

frequent determinations in case of increases toxicities grade 2, 3 or 4.

 Coagulation tests: Coagulation monitoring will be performed in patients on anticoagulant drugs treatment. During the treatment at the discretion of the investigator or if the patient is receiving anticoagulants.

#### **Pregnancy test:**

All women with reproductive capacity MUST have a negative urine pregnancy test within 72 hours before receiving study treatment. The minimum sensitivity of the pregnancy test should be 25 IU/L or equivalent units of HCG. If the urine pregnancy test is positive, a blood test should be done and if this pregnancy test in serum is positive, the patient should not receive study treatment and should not be included in the study.

#### **Disease evaluation**

#### Radiological Assessment of Tumour Lesions

Body CT-scan and contrast enhanced brain MRI will be performed baseline and every 8 weeks (+/-1 week) up to 12 months and according to normal practise thereafter.

In addition, CT/MRI scans must be obtained of anatomic regions not covered by the chest and abdomen scans, in subjects where there is clinical suspicion for deep soft tissue metastases (e.g., lesions in the thigh). Such additional CT/MRIs will be required at Screening only when deep soft tissue disease is and must be consistently repeated at all tumour assessment visits if a deep soft tissue lesion is identified during Screening. In cases without suspicion for deep soft tissue disease, no such CT/MRIs are required.

Similar methods of tumour assessment and similar techniques must be used to characterize each identified and reported lesion at Screening during the treatment evaluation phases. Imaging-based evaluation is preferred to clinical examination. Helical (spiral) CT scans of chest and abdomen are preferred. If not available, conventional (non-spiral CT) should be used. If not contraindicated, IV contrast should be used for all studies. If IV contrast is contraindicated, MRI should be used at the Screening exam and at all tumour assessment time points. Oral contrast should be used for all applicable imaging unless contraindicated.

A reference measurement ruler must be printed on every image for scale determination. Sections should be contiguous, similarly sized and consistent from visit-to-visit. Section thickness must be based on institutional standards (e.g., from 5 to 8 mm, 10 mm cuts are not recommended). Chest x-rays and ultrasound are not acceptable methods to measure disease. Response and progression of disease must be documented by CT or MRI like the methods used at Screening.

Screening bone scans are not mandatory and should be performed as clinically indicated. Abnormal findings on Screening bone scans, consistent with malignant disease, require follow-up bone scans in specified intervals. Normal bone scans at Screening do not require follow-up bone scans, except when clinically indicated. Abnormal bone scans should be confirmed with radiographic plain films, CT or MRI. Similarly, progressive disease based only on new lesion(s) found on bone scans must be supported with plain films, CT or MRI imaging studies of the bone lesion(s) to confirm their malignant nature. Increased intensity of uptake in previously abnormal areas on bone scans is not considered progressive disease, unless the lesions seen on the correlative imaging studies confirm the finding of disease progression. New areas of abnormal uptake on a bone scan represent disease progression.

Out of the assessments indicated by protocol, patients can be assessed whenever the investigator considers it indicated.

• Intracranial tumour response evaluation of brain lesions will be conducted, according to modified RECIST 1.1 criteria until disease progression, more information is detailed in section 10.3.

•

#### Non-radiological Assessments

Visible cutaneous lesions must be measured clinically. Digital and standardized photographic images including a ruler for scale as part of the image are recommended for documentation. All clinical assessments must be performed within proximity (± 7 days) of any protocol specified radiographic assessments

**Safety evaluation:** Safety assessments and adverse events include tumour-related, unrelated and treatment-related signs and symptoms. Adverse events will be documented and recorded in the CRF upon patient notification. AEs will be collected from the signing of Informed Consent until the end of treatment visit (30 days after end of treatment) or up to resolution. Classification of toxicity will be done according to the common terminology criteria for adverse events of the National Cancer Institute, version 4.03 (NCI CTCAE v. 4.03).

**PFS follow-up:** Body CT-scan and contrast enhanced brain MRI will be performed baseline and every 8 weeks (+/-1 week) up to 12 months and according to normal practice thereafter **until disease progression**, **independently of the end of treatment reason if it was not the documentation of disease progression**.

**OS Follow-up:** After disease progression all patients will be monitored to determine subsequent antineoplastic treatments and survival. It is recommended to maintain contacts by phone or by other methods every 4 weeks to carry out timely follow-up (up to 24 months or study closure).

**New anti-cancer therapy:** Information on subsequent treatments should include the list of post-treatment treatments, the drugs administered, and the date of initiation and discontinuation of each drug. All data will be recorded in the medical record and in the eCRF.

